of castrate resistant disease is almost invariably associated with some extent of tumor infiltration into the bone marrow. There is evidence of increased expression of androgen converting genes in the castrate-resistant bone marrow tumor microenvironment.

MD Anderson Experimental observation:

We recently discovered that prostate cancer cells, especially those that had metastasized to bone, overexpress fibroblast growth factor 9 (FGF9), a discovery that prompted us to study how FGF9 participates in prostate cancer progression and metastasis. FGF9 (also known as glial activating factor) is a secreted, glycosylated 26-kDa protein that has mitogenic effects on a variety of different cell types. In the normal prostate, FGF9 is not expressed by prostate epithelial cells, but is expressed by prostate stroma cells [21]. We have recently found positive staining for FGF9 in prostate cancer cells in 24 of 56 primary tumors derived from organ-confined prostate cancer and in all the bone metastases cases studied (25 of 25) (Table 1 and Figure 1). Findings were confirmed by RT-PCR analysis of RNA obtained by laser capture microdissection of normal prostate epithelial cells and prostate cancer epithelial cells derived from two bone metastases (Figure 1a). This switch in the source of FGF9 from the stroma to the cancer cells could increase the availability of FGF9, thereby favoring prostate cancer growth or survival at metastatic sites (**Li, et al. 2008**).

Primary Prostate Cancer

Bone Metastases of Prostate Cancer

Figure 1a. Fibroblast growth factor 9 (FGF9) expression in a normal prostate and prostate cancer. Upper panels and lower left and middle panels, immunohistochemical staining with antibody to FGF9 in normal prostate, two cases of organ confined primary prostate cancer (one positive and one negative for FGF9 expression) and two cases of bone metastases of prostate cancer. Original magnification 200x. Lower right panel, reverse-transcription polymerase chain reaction analysis of FGF9 expression in normal prostate (NP) and two case of bone metastases of prostate cancer (BM). gapdh - glyceraldehyde-3-phosphate dehydrogenase.

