2.0 STUDY OBJECTIVES

2.1 Primary Objective

The primary objective of this study is:

- To estimate overall survival and early response as characterized by a drop in PSA
- To identify the PSA modulation in 40 selected patients with advanced prostate cancer, and to correlate PSA Modulation with changes in bone remodeling markers.

Secondary Objectives

The secondary objectives of this study are:

- To estimate the objective tumor response rate for subjects with measurable disease at baseline.
- To explore the potential association between serum PSA and bone turnover markers with bone marrow FGF R 1 and FGF9 while on TKI 258
- To explore the predictive values of baseline FGF R 1, FGF9, and FGF signaling in serum and those in the bone marrow before and during treatment with TKI258
- To identify candidate mRNA gene expression changes in bone marrow biopsy aspirate following treatment with TKI258
- To collect and archive bone marrow biopsies and aspirates, serum and plasma in study patients for later hypothesis generating associations
- To explore FGF R expression following eight weeks of TKI 258.

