4.1 Inclusion Criteria

Each patient must meet the following criteria to be enrolled in this study.

- 1) Histologically proven adenocarcinoma of the prostate with evidence for skeletal metastases on bone scan and/or CT scan.
- 2) Eastern Cooperative Oncology Group (ECOG) performance status ≤ 2 . (Karnofsky Performance Status $\geq 50\%$) (Appendix F)
- 3) Serum testosterone levels \leq 50ng/ml

- 4) Ongoing gonadal androgen deprivation therapy with LHRH analogues or orchiectomy. Patients, who have not had an orchiectomy, must be maintained on standard dosing of LHRH analogue therapy at appropriate frequency for the duration of the study
- 5) Progression of disease despite androgen ablation (either documented osseous or soft tissue metastatic disease progression or by PSA criteria progression).
 - a) Definition of Progressive disease by PSA evidence: a PSA level of at least 5 ng/ml which has risen on at least 2 successive occasions, at least 2 weeks apart. The participant will need a baseline test and a test to show that the PSA has increased.
- 6) Discontinue diethylstilbestrol (DES) for ≥ 4 weeks and antiandrogens ≥ 6 weeks prior to study drug.
- 7) Discontinue any steroids prescribed to specifically treat prostate cancer (for e.g as a secondary hormonal manipulation or for cord compression) ≥ 4 weeks prior to study drug. Steroids chronically prescribed for a non-cancer-related illness (e.g. asthma or COPD) that is well controlled with medical management are permissible to an equivalent of ≤10 mg Prednisone daily.
- 8) Antiandrogen Withdrawal: Patients who are receiving an antiandrogen as part of primary androgen ablation must demonstrate disease progression following discontinuation of antiandrogen. Disease progression after antiandrogen withdrawal is defined as 2 consecutive rising PSA values, obtained at least 2 weeks apart, or documented osseous or soft tissue progression.
- 9) For patients receiving flutamide, at least one of the PSA values must be obtained 4 weeks or more after flutamide discontinuation.
- 10) For patients receiving bicalutamide or nilutamide, at least one of the PSA values must be obtained 6 weeks or more after antiandrogen discontinuation
- 11) Laboratory Requirements:
 - Adequate adrenal function (absence of symptoms or electrolyte imbalances that indicate adrenal insufficiency).
 - WBC count \geq 3,000/µl
 - Absolute Neutrophil Count (ANC) \geq 1,500/µl
 - Hemoglobin ≥ 8.0 g/dL independent of transfusion

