10.0 PLANNED STATISTICAL METHODS

This is a phase IIA activity trial of TKI258 for treatment of castrate resistant prostate cancer with skeletal metastases. The two primary outcomes are survival time and early response as characterized by a drop in PSA as defined by working group criteria. Based on historical mean survival time 8 months, a mean survival time on average > 10 months with TKI258 would be considered promising evidence of anti-disease activity. The planned sample size is 40 patients, with an anticipated accrual rate of 3 patients per month. Based on historical experience using carefully selected candidates with evidence for iliac involvement on bone scan, we anticipate that ~60% of patients will have positive biopsies. No early stopping rule in terms of the probability of PSA response will be employed because it is not known whether blocking the stromal-epithelial interactive pathway (SE-pathway) will be related to clinical benefit. Consequently, it may be the case that PSA does not drop but survival time is prolonged due to inhibition of disease progression by TKI258. Given the short survival time of these patients and anticipated accrual rate of 3 patients per month, it also will not be

feasible to implement an early stopping rule in terms of observed survival times. Based on an historical rate of 20% grade 3 or 4 toxicity with standard therapies the method of Thall and Sung (1998) will be used to monitor toxicity. Unadjusted survival time will be estimated using the method of Kaplan and Meier (1958) and the effects of the following four potential prognostic covariates: Inhibition of FGF signaling by bone marrow biopsy at 4 weeks, modulation of the bone markers (a) urinary NTX and (b) bone specific alkaline phosphatase, and baseline signature of FGF signaling in terms of FGF R-1, FGF R-3 and FGF 9 on Prob(PSA response) will be estimated using logistic regression, and on survival time will be estimated using the Cox model or an appropriate time-to-event regression model.

Preliminaries: This is a phase IIA activity trial of TKI258 for treatment of castrate resistant prostate cancer with skeletal metastases. The two primary outcomes are survival time and early response as characterized by a drop in PSA as defined by working group criteria (25).

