Data Analysis. If the data on the 40 patients yield a sample mean of 10 months (the targeted 25% improvement) based on total follow-up time 400 months (all 40 deaths observed) then the posterior of m would be IG(42.064, 408.512), which has mean 9.95 months and posterior 95% credible interval 7.33 - 13.4 months. Similarly, if 35 deaths are observed with 5 death times administratively censored and total follow-up 460 months at the final analysis then the posterior of m would be IG(37.064, 468.512),), which has mean 13 months and posterior 95% credible interval 9.39 - 17.95 months. Unadjusted survival time will be estimated using the method of Kaplan and Meier (27). The effects of the following four potential prognostic covariates on Prob(PSA response) will be estimated using logistic regression (28), and on survival time will be estimated using the Cox model or, if the proportional hazards assumption is not satisfied, using an appropriate time-to-event regression model chosen based on preliminary goodness-of-fit analyses of the data (29). Each of the following covariates is a binary indicator.

- 1. Inhibition of FGF signaling by bone marrow biopsy at 4 weeks.
- 2. Modulation of the bone markers (a) urinary NTX and (b) bone specific alkaline phosphatase
- 3. Baseline signature of FGF signaling in temrs of FGF R-1, FGF R-3 and FGF 9.

Time of disease progression if defined by PSA alone is defined as follows: Three consecutive PSA elevations above nadir or baseline are required. Each increment in PSA should be a minimum of 1 ng/ml and at least 2 weeks apart or will not count. The time of PSA progression will be taken as the time of the first of these PSA elevations that represents an increment by at least 25% above the nadir or baseline. Given that increments in PSA do not always represent treatment failure, particularly when novel agents with uncertain effects on PSA levels are being evaluated, clinical and radiological correlation is recommended at the discretion of the treating physician. In patients with PSA progression alone without clinical or radiological evidence of disease progression, continued therapy on study is at the discretion of the treating physician in consultation with the principal investigator.

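### The baseline FGF signature is a yes/no covariate with no stated specimen, cut-point or combination rule; if FGF9 is scored by tumour-cell staining it will be near-constant, and measured levels would serve better

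*Combined protocol and SAP*

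**What the plan says.** The Data Analysis part of Section 10.0 relates a short list of covariates to PSA response (logistic regression) and to survival (Cox or another time-to-event model). It says of the list that "Each of the following covariates is a binary indicator". The last item is "Baseline signature of FGF signaling in temrs of FGF R-1, FGF R-3 and FGF 9". No specimen, assay, threshold or rule for combining the three markers is given, and nothing is said about patients whose marrow biopsy shows no tumour.

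Four other places bear on this:

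- Section 1.2 reports FGF9 staining in cancer cells in "24 of 56 primary tumors derived from organ-confined prostate cancer" and "in all the bone metastases cases studied (25 of 25"). It adds: "In the normal prostate, FGF9 is not expressed by prostate epithelial cells, but is expressed by prostate stroma cells".
- Section 4.1, item 1, requires "evidence for skeletal metastases on bone scan and/or CT scan".
- Section 10.0 states: "we anticipate that ~60% of patients will have positive biopsies".
- The secondary objectives in Section 2.0 include this aim: "To explore the predictive values of baseline FGF R 1, FGF9, and FGF signaling in serum and those in the bone marrow". That objective carries no coding instruction.

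**The concern.** FGF9 is the main disease-specific rationale for the drug in Section 1.2, and its predictive value at baseline is a secondary objective. The only FGF9 positivity data in the documents are a yes/no staining call. That call varied in organ-confined primaries but not at all in bone metastases, and every enrolled patient must have skeletal metastases. A yes/no signature that used the same call could carry a component that hardly varies.

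Two things are at stake. The signature could be reported as a test of FGF9 when only the two receptors, or nothing, separate the patients. And if tumour-negative marrows are coded FGF9-negative, a difference between marrow-involved and marrow-free patients could be read as an FGF9 effect. Even if FGF9 is measured as a level, the plan as written turns it into two groups.

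**Working it through.** **Inputs.** From Section 1.2: 25 of 25 bone metastases and 24 of 56 primaries FGF9-positive. From Section 10.0: 40 patients, about 60% with positive biopsies. The plan gives no prevalence, power or effect size for the covariate analyses, so there is no planned figure to reproduce beyond the raw proportions: 25/25 = 100% and 24/56 = 42.9%.

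**Step 1. Patients by marrow status.** 0.60 × 40 = 24 tumour-positive; 40 − 24 = 16 tumour-negative.

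**Step 2. How many FGF9-negative patients, if the call is tumour-cell staining?** With 25 of 25 positive, the exact lower limit for the positive proportion is 0.025^(1/25) = 0.863 (two-sided 95%) or 0.05^(1/25) = 0.887 (one-sided 95%). The negative proportion is therefore 0 at the point estimate and at most 1 − 0.863 = 0.137 at the two-sided limit. Among 24 patients that is 0 to 24 × 0.137 = 3.3 expected negatives.

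A prediction that carries the uncertainty of the 25 cases agrees:

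- Uniform prior: the chance that all 24 are positive is 26/(26 + 24) = 0.52. The expected number of negatives is 24 × 1/27 = 0.9, and the chance of at most 2 is 0.90.
- Jeffreys prior: the chance that all 24 are positive is 0.72.

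**Step 3. What remains of the signature when FGF9 is positive in everyone?** Let r1 and r3 be the proportions positive for FGFR-1 and FGFR-3. The documents give neither; 30% to 70% each, independent, is assumed.

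| Rule | Share signature-positive | Range |
|---|---|---|
| Any marker positive | 1 | 100% (no contrast) |
| All three positive | r1 × r3 | 0.3 × 0.3 = 9% to 0.7 × 0.7 = 49% |
| Two of three positive | r1 + r3 − r1 × r3 | 0.6 − 0.09 = 51% to 1.4 − 0.49 = 91% |

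Under the last two rules the signature still separates patients, but only through the receptors. Two of three becomes either receptor positive.

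**Step 4. The tumour-negative biopsies.** With no cancer cells in the specimen, tumour-cell FGF9 is missing or is called negative. If it is called negative, the FGF9-negative group holds these 16 plus 0 to 3.3 true negatives. Absence of tumour then explains between 16/19.3 = 83% and 16/16 = 100% of the negative calls. If host cells in the marrow were counted instead, the call would not measure tumour FGF9 either; the plan does not say which compartment counts.

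**Step 5. Illustration of the cost of imbalance.** Assume an FGF9-alone Cox contrast in the 24 tumour-positive patients, all of whom die, at two-sided 5%. Power = Φ(√(24 × q × (1 − q)) × ln HR − 1.96), where q is the FGF9-negative share.

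| FGF9-negative patients | HR 2 | HR 3 |
|---|---|---|
| 1 of 24 | 10% | 19% |
| 3 of 24 | 20% | 43% |
| 12 of 24 | 40% | 77% |

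The hazard ratios, the 5% level and the restriction to 24 patients are assumptions, and the plan does not contain this contrast. The table shows direction only.

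**Step 6. If FGF9 is a level.** A high/low cut can divide patients even when every metastasis stains. It treats all values on one side of the cut as equal, and because no cut-point is stated it could be chosen after seeing the outcomes of 40 patients.

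**The case against.** The strongest objection is that Section 10 never says FGF9 will be scored by tumour-cell staining. The study title points to marrow plasma, and the secondary objective covers serum as well as marrow. A binary indicator may simply be a high/low split of a level. This stands, and it makes the staining argument conditional.

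A reader might infer something stronger: that FGF9 status cannot separate patients in this trial at all, or that the signature's value is settled by eligibility and marrow involvement. The documents do not support either. The specimen and cut-point are open, 25 of 25 is compatible with up to about 14% negative, and under two of the three natural rules FGFR-1 and FGFR-3 still produce a split.

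It is also fair to say that the planned covariate is a composite, so the power figures for FGF9 alone describe no planned model. Even an even split gives only 40% at a hazard ratio of 2, so sample size is the larger limit. The binary sentence governs the Section 10 list, not the secondary objective, for which levels remain open. Finally, the covariate relationships are described as exploratory.

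These points limit the size of the problem. They do not remove it: a binary coding is stated, it is undefined, and each reading considered here loses something.

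**Conclusion.** The point holds in a conditional form. The baseline signature is a yes/no covariate without a specimen, cut-point or combination rule. If FGF9 is scored by tumour-cell staining, expect about 0 to 3 FGF9-negative patients among some 24 with tumour-positive marrow. FGF9 then contributes almost nothing, and negative calls in the other 16 or so would reflect absent tumour. If FGF9 is a level, dichotomising it loses information that 40 patients can ill spare.

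The staining result assumes that the trial assay behaves like the one in Section 1.2, that the enrolled marrows resemble those 25 cases, and that about 60% of biopsies contain tumour.

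This is a worthwhile improvement to an exploratory analysis. It does not touch the decision rule on mean survival or the sample size of 40.

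**What to change.** In the Data Analysis part of Section 10.0:

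- Exempt the baseline FGF signature from the sentence that makes every covariate binary.
- Enter baseline FGF9, FGFR-1 and FGFR-3 as measured levels, one marker per model given the sample size. Examples are the log marrow-plasma or serum level, or a graded staining score where tumour is present. Name the specimen and assay for each.
- Do not use FGF9 positive/negative staining as a component of any signature.
- Include marrow tumour status as its own variable, and treat tumour-cell staining in tumour-negative biopsies as not assessable.

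No patients or visits are added: Sections 7.1 and 7.2 already schedule baseline marrow and blood for biomarkers. There are three costs. Effects are reported per unit or per SD, not as a yes/no contrast. Section 7.1 lets patients rely on marrow taken within 12 weeks before treatment, with stored tissue requested where it was banked, so those without a usable baseline marrow sample contribute only blood-based levels. And the documents describe no quantitative FGF9 assay, so if none is in place one has to be specified.
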